We are proposing a double-blind, placebo-controlled study that enrolls young adult smokers stratified for menthol preference. Menthol and control flavor will be delivered via an e-cigarette just prior to saline or IV nicotine infusion. This menthol / nicotine reinforcement study was preceded by a separate menthol dose-finding study that determined the low and high doses of menthol to be administered by the e-

[Type text]

[Type text]

cigarette. For this dose-finding study, subjects were screened at the West Haven site where the IV nicotine study will be performed, but the dose-finding study was conducted at the John Pierce Labs located on the Yale Campus located about 2 miles from the West Haven site. The screening procedure for the dose-finding study was described in a separate screening consent form. The dose-finding study did not administer any nicotine.

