For this menthol / nicotine reinforcement study, the Test Sessions will be conducted after an Adaptation Session is completed where subjects will learn to use the e-cigarette for delivering the menthol or control (tobacco) flavor. A short e-cigarette questionnaire will also be administered during the Adaptation Session. Then, the nicotine Test Sessions will be performed following overnight abstinence from tobacco. Smokers will be assigned a random sequence of three different e-cigarette conditions (low menthol (0.5% or 5 mg/mL) plus tobacco flavor, high dose menthol (3.5% or 35 mg/mL) plus tobacco flavor or tobacco flavor alone for each of the three Test Sessions (a different menthol condition for each session). The concentration of tobacco flavor will be identical across all conditions. The amount of menthol in high dose condition is the same as those found in commercially available mentholated e-cigarette solutions (AmericaneLiquidStore™). The low dose menthol solution contains menthol that is minimally perceptible by smokers and is in the range of e-cigarette solutions targeting smokers with a preference for low menthol impact in the e-cigarette vapor. In each Test Session, smokers will receive a random order of one intravenous delivery of saline, and two intravenous deliveries of nicotine (3.6 mcg/kg and 7 mcg/kg or 0.25 mg/70 kg and 0.5 mg/70kg), just after the menthol or control flavor is delivered via the e-cigarette. The intravenous dose deliveries will be one hour apart to provide sufficient time for the nicotine and menthol effects to wear off. The nicotine infusion sessions will be at least 24 hours apart to minimize carryover nicotine effects. The main outcome measure will be subjective drug effects as measured with the Drug Effects Questionnaire (DEQ). Other outcomes include cardiovascular measures, cognitive performance, and self-report measures of nicotine withdrawal. Cardiovascular measures include heart rate, systolic and diastolic blood pressure. Cognitive performance will be assessed with the Stroop test, mathematical processing test (MPT), and continuous performance test (CPT). Nicotine withdrawal measures will be measured with the Nicotine Withdrawal Symptom Checklist (NWSC) and the Brief Questionnaire on Smoking Urges (BQSU).

B. Dose Finding Study

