- d) Other measures: We recognize the value of banking biological samples for future genetic, epigenetic and biomarker analyses given the care taken to establish clinical phenotypes. For example, results from genetic studies may confirm the importance of certain TRP-ion channels, or sweet taste receptors, in the effects of menthol and sweeteners on initiation and maintenance of nicotine addiction. These findings would provide a rationale for examining established and novel

[Type text]

[Type text]

genetic variants of TRP-channels, and sweet taste receptors, as determinants of responses to flavors in the laboratory. Whenever specific hypotheses are generated in the future that require targeted genetic analysis, this protocol will be amended to describe the purpose and use of such analyses.

E. Drugs

a) Nicotine: Nicotine bitartrate will be obtained from Interchem Corporation, Paramus, NJ. Nicotine samples will be prepared by the research pharmacy at the West Haven VA. Common side effects of nicotine include nausea, vomiting, heartburn, elevated heart rate and increased blood pressure.

- IV Nicotine Administration: Nicotine will be administered over 30 seconds using a syringe that is attached to an IV catheter located in a forearm vein. We have followed these procedures in our previous studies (Sofuoglu *et al.* 2005, 2006b; 2008a, 2009a,b,c) which were completed without any serious and unexpected adverse effects attributed to nicotine, or with other safety concerns. After the last dose, the subjects will stay in the lab for at least three hours, which has been shown to be sufficient for the nicotine-induced changes in heart rate, blood pressure, and subjective effects to return to baseline (Sofuoglu *et al.* 2005; Sofuoglu *et al.* 2006).
- Justification for the nicotine doses: For this proposal, we chose two dose sequences of nicotine (3.6 mcg/kg and 7 mcg/kg or 0.25mg/70 kg and 0.5mg/70kg) with a maximum dose of 0.3 mg and 0.6 mg, respectively, regardless of body weight. In a previous study, these nicotine doses produced robust subjective and physiological responses (Sofuoglu *et al.* 2009a). However, the doses used in this study are much lower than doses used in previous studies with addicted smokers (up to 3 mg per injection). Therefore, we believe that the doses used in this study represent an appropriate balance between being sufficiently high to answer the research questions, but low enough to reduce risks to the study participants.

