- b) Test Sessions: Experimental sessions will start around 8:30 AM. As summarized in Table 2, baseline biochemical measures will include urine menthol glucuronide and cotinine, plasma nicotine, and for women, estradiol and progesterone levels. These samples will be obtained followed by cognitive testing. Subjects will then start inhaling from the e-cigarette with the assigned menthol condition (control flavor, low or high dose of menthol), one inhalation every 15 seconds as practiced in the adaptation session. It will take approximately 90 seconds to complete 6 inhalations. Subjects will then receive the first delivery of the assigned injection (saline, 0.25 mg/70 kg or 0.5 mg/70 kg nicotine). Each study injection will be 60 minutes apart to provide sufficient time for the physiological and subjective nicotine effects to return to baseline. Following each injection, physiological, subjective, and cognitive outcome measures will be obtained.
- c) Medical monitoring: For nicotine test sessions, a physician will be present and subjects will be attached to a blood pressure and heart rate monitoring device. An IV catheter will be in place throughout the session. Subjects will be administered nicotine only if the systolic blood pressure is <150 mmHg and heart rate is <100 beats/minute. Subjects will be terminated from the study if the blood pressure at any time is >170/110 mm Hg, the heart rate is >120 beats/min, or if they develop signs and symptoms compatible with nicotine toxicity. Subjects

[Type text]

[Type text]

will remain in the laboratory for three hours after the last nicotine administration. These procedures have been developed as part of our IND application for IV nicotine.

Table 2. Schedule of Events: Experimental Session*

Time	Measures and Events
8:00 AM	(Building 36) CO level, urine sample, BAL, and light standard breakfast
9:00 AM	(Biostudies Unit) blood sample. HR/BP, EKG, M-NWSC, BQSU, SAFTEE, Cognitive Testing
11:00 AM	Menthol (control, high or low Menthol) DEQ + IV Saline or Nicotine (0.25 or 0.5mg/70 kg) blood draw
11:01	HR/BP, DEQ
11:02	HR/BP
11:03	HR/BP, DEQ,
11:05	HR/BP, DEQ
11:08	HR/BP, DEQ blood draw
11:10	HR/BP, DEQ
11:15	HR/BP, DEQ, Cognitive Testing
11:30	HR/BP, DEQ blood draw
11:45	HR/BP, DEQ
11:55	HR/BP, DEQ, BQSU
12:00	Menthol (control, high or low Menthol) DEQ + IV Saline or Nicotine (0.25 or 0.5 mg/70 kg), blood draw
13:00	Menthol (control, high or low Menthol) DEQ + IV Saline or Nicotine (0.25 or 0.5 mg/70 kg), blood draw

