14:00 noon	HR/BP, EKG, M-NWSC, BQSU, SAFTEE

[Type text]

[Type text]

15:00 PM	End of session, collection of urine sample, blood draw Discharge
----------	---

*The same measures will be obtained following saline and each nicotine administration. For brevity, only the measures after saline are shown. Abbreviations: CO: Alveolar carbon monoxide; HR/BP: Heart rate/Blood pressure; EKG: Electrocardiogram; M-NWSC: Minnesota Nicotine Withdrawal Symptom Checklist; BQSU: Brief Questionnaire of Smoking Urges; DEQ: Drug Effects Questionnaire; SAFTEE: Systematic Assessment for Treatment Emergent Events.

12. Data analysis methods

Data analyses: The primary analyses will be intent-to-treat and will include all available data on subjects who complete at least one test day. Mixed-effects models will be used to test the study hypotheses. These models allow for different numbers of observations per subject, use all available data on each subject, and are unaffected by randomly missing data. They also provide flexibility in modeling the correlation structure of the data. All data will be checked for normality and transformations will be applied as necessary. Significance level of 0.05 will be used for the main hypotheses and Bonferroni correction will be applied for post-hoc tests.

Specific Aim #1: To determine if menthol administered via e-cigarettes will change the reinforcing effects of pure nicotine administered intravenously in cigarette smokers who smoke mentholated or non-mentholated cigarettes. The reinforcing drug effects will be measured with the DEQ.

Hypothesis #1A: Concurrent menthol and nicotine administration will lead to greater reinforcement than nicotine and control flavor, saline and menthol, or saline and control flavor conditions.

Hypothesis #1B: Enhancement of nicotine reinforcement by menthol will be greater in menthol smokers than in non-menthol cigarette smokers.

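### Table 2 discharges subjects two hours after the third infusion, one hour short of the protocol's three-hour stay whenever that infusion is nicotine (4 of 6 possible orders)

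*Protocol*

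**What the plan says.** The Protocol states the post-nicotine stay in two places. Study Procedures c), on medical monitoring, says that subjects "will remain in the laboratory for three hours after the last nicotine administration". Section 11.E a), under IV nicotine administration, says: "After the last dose, the subjects will stay in the lab for at least three hours". The sentence after the first statement reads: "These procedures have been developed as part of our IND application for IV nicotine".

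Table 2 gives the session timetable. The 11:00 row reads "Menthol (control, high or low Menthol) DEQ + IV Saline or Nicotine (0.25 or 0.5mg/70 kg) blood draw", and the 12:00 and 13:00 rows carry the same event, so each infusion may be saline or either nicotine dose. The 15:00 row reads "End of session, collection of urine sample, blood draw Discharge". Section 11.A explains why the third infusion may be nicotine: in each session "smokers will receive a random order of one intravenous delivery of saline, and two intravenous deliveries of nicotine".

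Section 11.C adds a related figure. It says that subjects are monitored for two hours after the last nicotine.

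**The concern.** A session run to the printed times cannot deliver the stated stay when nicotine is given at 13:00. Session staff are likely to work from the timetable, so the shorter interval is the one that would happen in practice. The protocol would then miss its own post-nicotine observation commitment in most of the possible infusion orders, and one of the two statements of that commitment is linked to the IND procedures.

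What is at stake is compliance with a safety procedure. The scientific conclusions are not at risk: the last DEQ time point in the primary model is 55 minutes after infusion, well inside either interval.

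**Working it through.** **Inputs**

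- Required stay: 3 h after the last nicotine (Study Procedures c); at least 3 h after the last dose (section 11.E a).
- Infusion times: 11:00, 12:00 and 13:00 (Table 2), consistent with the 60-minute spacing in Study Procedures b).
- Discharge: 15:00 (Table 2).
- Infusions per session: one saline, nicotine 0.25 mg/70 kg and nicotine 0.5 mg/70 kg, in random order (section 11.A).

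**Formula**

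Scheduled stay = discharge time − time of last nicotine infusion. Shortfall = 3 h − scheduled stay. The number of possible orders is 3! = 6.

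| Order (11:00, 12:00, 13:00) | Last nicotine | Stay to 15:00 | Shortfall |
|---|---|---|---|
| saline, 0.25, 0.5 | 13:00 | 2 h | 1 h |
| saline, 0.5, 0.25 | 13:00 | 2 h | 1 h |
| 0.25, saline, 0.5 | 13:00 | 2 h | 1 h |
| 0.5, saline, 0.25 | 13:00 | 2 h | 1 h |
| 0.25, 0.5, saline | 12:00 | 3 h | 0 |
| 0.5, 0.25, saline | 12:00 | 3 h | 0 |

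The three-hour figure is met in 2 of 6 orders and missed by 1 h (1/3 of the stated stay) in the other 4.

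**Can another reading close the gap?**

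- *Start time.* Study Procedures b) has sessions starting at about 8:30, while Table 2 starts at 8:00. Shifting the whole day moves the third infusion and discharge together, so the interval between them remains 2 h.
- *Table footnote.* It says that measures repeated after each infusion are omitted for brevity. It does not extend the session beyond 15:00.
- *Meaning of last dose in section 11.E.* If it means the last infusion of any kind, the interval is 15:00 − 13:00 = 2 h in every session and all 6 orders are short. The count of 4 is therefore the conservative one.

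**What would satisfy the text**

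13:00 + 3 h = 16:00. The scheduled session then lasts 8 h (8:00 to 16:00) in place of 7 h (8:00 to 15:00). That adds 1 h per session and 3 h for a subject who attends all three.

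**The case against.** The best counter-argument is that Table 2 may not be the outlier. Section 11.C and Study Procedures c) are near-duplicates, with the same blood pressure and heart rate limits and the same catheter and physician provisions. They end in parallel sentences, one giving two hours and the other three. Table 2 matches the two-hour figure exactly. On this view the text conflicts with itself, and changing it to two hours would be as good a repair as moving discharge. The IND remark does not settle the matter, because the IND is not shown.

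Part of this stands: the protocol does not prove which figure was intended. However, section 11.C concerns how long subjects are monitored, while the other two places concern how long they stay. Two hours of monitoring fits inside a three-hour stay, so section 11.C need not be wrong. Discharge at 15:00 cannot be reconciled with a three-hour stay after nicotine at 13:00. Three hours is also stated twice, and section 11.E supports it by citing earlier IV nicotine studies. It is the cautious choice.

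A second objection is that the last dose in section 11.E, read in its nicotine context, means nicotine, so the all-orders reading is weak. That is reasonable, and the conclusion does not depend on that reading.

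A third is that the point is only editorial. Its weight is indeed small. The protocol itself treats an hour as enough between infusions: "Each study injection will be 60 minutes apart to provide sufficient time for the physiological and subjective nicotine effects to return to baseline". Section 11.E calls three hours sufficient, which does not imply that two hours is inadequate.

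**Conclusion.** The inconsistency is real. As printed, Table 2 gives 2 h against a stated 3 h in the 4 of 6 possible orders that end with nicotine, and exactly 3 h in the 2 that end with saline. The count covers possible orders and assumes nothing about how often each occurs. It takes the Table 2 clock times at face value and reads the requirement as running from the last nicotine infusion.

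Severity is minor. Nothing in the protocol shows that two hours is unsafe, and power, sample size and the primary DEQ analysis are unchanged.

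**What to change.** Move discharge in Table 2 to 16:00 or later in every session. Use one fixed time: section 11.A describes the study as double-blind, so staff cannot release subjects earlier on the grounds that saline came last.

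Add a sentence saying when the samples now listed at 15:00 are taken: at 15:00 (2 h after the third infusion) or at the new discharge time (3 h after it, if that is 16:00). This needs stating because section 11.D takes the final blood sample just before the IV is removed, Study Procedures c) keeps the IV in for the whole session, and section 11.G takes an mRNA sample at session end. If session end and discharge remain one event, the blood samples move with it. If the session and IV end at 15:00 and only discharge moves to 16:00, the samples stay where they are. Either is workable.

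For consistency, section 11.C could state the three-hour stay alongside its two-hour monitoring period.

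The edits are one clock time, one sentence and one optional wording change. The practical cost is an extra hour per session (three over the study for a subject who attends all sessions). If the whole session is extended, the IV stays in longer, a physician has to be present for longer, and the end-of-session lunch comes an hour later. Neither the sample size nor the primary analysis changes.

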- Subjective Drug Effects: 1) Drug Effects Questionnaire (DEQ), adapted from Soria (1996), will be used during the test session to measure acute drug responses including: liking, cooling, irritation, strength, feeling, stimulation, good effects, bad effects, head rush, and want more. Each item is rated on a 100 mm scale, from 'not at all' to 'extremely'.
- Drug Use: Self-reports of cigarette smoking and use of other tobacco products, alcohol and drugs (cocaine, alcohol, opioids, marijuana, and other illicit drugs) will be assessed with Time Line Follow-Back, which has been shown to be a reliable and valid method for monitoring substance use and other outcomes in longitudinal studies (Miller and DelBoca, 1994; Sobell and Sobell, 1992). The Time Line Follow-Back will be administered at intake.
- Adverse events: SAFTEE: In order to monitor adverse events from the study medications, the SAFTEE will be administered before and after each session. The SAFTEE has been used in a number of pharmacotherapy trials (Levine and Schooler, 1986).
- Cognitive Performance: Cognitive performance will be assessed with 3 tests from the ANAM battery (University of Oklahoma): the Stroop test, the mathematical processing test (MPT), and the continuous performance test (CPT). These 3 tests were chosen because of their sensitivity to tobacco withdrawal and nicotine administration (Heishman *et al*, 2010; Mancuso *et al*, 1999; Myers *et al*, 2008).
 - Stroop Test: This test assesses processing speed, selective attention, and interference (Spreen, 1991). It is a computerized version of the classical Stroop Test (Reeves, 2002). The Stroop design consists of one three-minute block of congruent stimuli, and one three-minute block of incongruent stimuli.
 - Mathematical Processing Test (MPT): This test assesses basic computational skills, concentration, and working memory. An arithmetic problem involving three single-digit numbers and two operators is displayed (e.g., "5 - 2 + 3 ="). The subject presses buttons to indicate whether the answer to the problem is less than five or greater than five.
 - Continuous Performance Test (CPT): This test assesses sustained attention, concentration, and working memory. A target character is displayed for memorization. Then, as individual characters are displayed in sequence, the user presses a designated button only when the displayed character is the target letter.

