The main outcome measures will be the “good effects” and “drug liking” items of the DEQ. Mixed effects models will include the within-subject factors nicotine dose (0.25, 0.5 mg nicotine or placebo), menthol dose (low dose of menthol, high dose of menthol, or control flavor) and time of measurement (+1,+3,+5,+10,+15,+30,+45,+55 minutes); the between-subject factor types of cigarette preference (menthol vs. non-menthol) and all possible interactions among these factors. We will also consider order effects for nicotine dose (1, 2 or 3) and session day (1, 2 or 3) and the effects of potential covariates (race, sex, baseline plasma NMR, FTND scores). These effects will be included in the final model if significant. Estradiol and progesterone levels will also be considered as potential covariates in a secondary analysis of women only. We will consider several different correlation structures for the repeated measures within individuals, and will select the best fitting one based on Schwartz Bayesian information criterion. SAS PROC MIXED will be used for the mixed-model analyses.

A significant interaction between nicotine dose and menthol dose, with significantly higher response to menthol + nicotine compared to control flavor + nicotine or control flavor + saline will be considered supportive of hypothesis 1A. A significant interaction between nicotine dose, menthol dose, and group (menthol vs. non-menthol smokers), with significantly stronger effects in menthol smokers than in non-menthol smokers, will be considered supportive of hypothesis 1B. We expect significant effects for both doses and will also test for dose-dependent effects.

[Type text]

[Type text]

Rationale for sample size: Both studies have 80% power to detect large effect sizes ($f=0.4$) for the interactions of interest in repeated measures analysis with 30 subjects per group for a total of 60 subjects at 0.05 significance level. Our preliminary data for both outcome measures show larger magnitude effects for the nicotine effects (all $f>0.5$) and menthol effects are expected to be similarly strong (Sofuoglu et al. 2009a). Applying Bonferroni correction and using an alpha level of 0.01 we have 80% power to detect post-hoc comparisons of medium to large effect size $d'=0.7$ for the menthol and nicotine effects. Our previous study shows larger effects of nicotine $d'>1.0$. To account for up to 70% dropout we will recruit 160 subjects for a target of 60 completers.

13. Risks and benefits

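### The 1A criterion accepts an interaction of either sign and leaves out the menthol + saline comparison, and a data-driven choice of scale makes a less-than-additive result more likely to count as support.

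*Protocol*

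**What the plan says.** All of this is in the protocol, mainly Section 12 (Data analysis methods).

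- **Hypothesis 1A** is worded as an ordering: "Concurrent menthol and nicotine administration will lead to greater reinforcement than nicotine and control flavor". The sentence goes on to name two more comparators, saline with menthol and saline with control flavour.
- **Criterion for 1A**: "A significant interaction between nicotine dose and menthol dose", "with significantly higher response to menthol + nicotine compared to control flavor + nicotine or control flavor + saline". No sign is given for the interaction, and menthol + saline does not appear.
- **Criterion for 1B**: a three-way interaction, "with significantly stronger effects in menthol smokers than in non-menthol smokers". Here a direction is stated.
- **Scale**: "All data will be checked for normality and transformations will be applied as necessary". This covers the two primary items of the Drug Effects Questionnaire. Section 11.D(c) says of that questionnaire: "Each item is rated on a 100 mm scale".
- **Expected effects**: the sample-size paragraph says "menthol effects are expected to be similarly strong", next to nicotine effects of f above 0.5. Section 11.A qualifies this for one arm: "The low dose menthol solution contains menthol that is minimally perceptible by smokers".

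**The concern.** The 1A hypothesis and its criterion do not ask the same question. The hypothesis says the combination is rated above three other conditions. The criterion asks for an interaction of unspecified sign plus an ordering against two of the three. A negative interaction means that menthol adds less in the presence of nicotine than with saline. That is the opposite of enhancement, which is the premise of 1B, yet it would count as support for 1A.

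The scale rule adds to this. When both factors raise ratings, whether an interaction exists, and with which sign, depends on the scale. A square root or logarithm compresses the high cell most, so effects that add in mm become less than additive, and synergy in mm shrinks or disappears. A transformation is usually harmless for the direction of a main effect, but not for an interaction of this kind. At stake is whether a positive 1A finding means enhancement, and whether real enhancement in mm would be found.

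**Working it through.** **The plan's own figure.** Section 12 states 80% power at f = 0.4, N = 60, alpha 0.05. With noncentrality f²N = 0.16 × 60 = 9.6, power is 0.79 for 2 numerator degrees of freedom (116 error df) and 0.69 for 4 (232 error df), the full 3 × 3 interaction. The protocol states no degrees of freedom. The point here does not depend on this figure.

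**Notation.** Cell means in mm are given in the order control+saline (CS), control+nicotine (CN), menthol+saline (MS), menthol+nicotine (MN). The interaction is I = (MN − CN) − (MS − CS). The protocol gives no means, so all those below are assumed.

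**Step 1: sign and missing comparator, no transformation involved.**

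- 10/40/30/50: I = (50 − 40) − (30 − 10) = −10. MN exceeds CN (40) and CS (10), so the ordering in the criterion holds.
- 10/30/60/45: I = (45 − 30) − (60 − 10) = −35. MN exceeds CN (30) and CS (10), so the ordering holds again, although MN is below MS (60) and hypothesis 1A as worded is false.

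For 10/40/30/50, a simulation of 60 subjects with log-normal ratings (between- and within-subject SD 0.5 on the log scale, capped at 100, 4,000 runs, simple comparisons at 0.01) met the criterion with a negative interaction in 18% of runs in mm, 40% on the square-root scale and 42% on log(1+y).

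**Step 2: effect of scale on I.**

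| Cells | mm | square root | log |
|---|---|---|---|
| 10/25/25/40 | 0 | −0.51 | −0.45 |
| 10/30/20/40 | 0 | −0.46 | −0.41 |
| 10/20/20/40 | +10 | +0.54 | 0 |

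For example, 10/20/20/40 on the log scale gives ln(40 × 10) − ln(20 × 20) = 0.

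**Step 3: how often this matters.** Assumptions: gamma ratings of shape 2, capped at 100; within-subject correlation 0 to 0.5; n = 60; one 2 × 2 contrast. The choice rule is also assumed: keep mm if Shapiro-Wilk on the residuals gives p ≥ 0.05, otherwise take the most normal of mm, square root and log(x+1). The 1A rule was applied as interaction p < 0.05 of either sign, plus MN significantly above both CN and CS at 0.01, the post-hoc level in Section 12.

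| Cells | Outcome | Chosen scale | mm |
|---|---|---|---|
| 10/25/25/40 (additive) | 1A rule met | about 12–40% | 3–4% |
| 10/30/20/40 (additive) | 1A rule met | about 1–15% | 2–3% |
| 10/20/20/40 (synergy) | power | about 23–36% | 63–89% |

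In the first row almost all chosen-scale successes have a negative interaction. The mm test rejected in 4–6% of additive trials despite the skewness, so no transformation was needed to hold the error rate.

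**Step 4: where the effect fades** (chosen-scale rate of a significant interaction, additive cells).

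- Weak menthol, 10/30/12/32: 6–9%.
- Ratings well above the floor, 25/40/40/55: 6–7%.
- Near-normal ratings (SD 10): mm kept in 97–98% of trials, about 6%.

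**The case against.** **The percentages are not false positives.** A reader might take 12–40% as a type I error rate for 1A. The documents do not support that. Section 12 words 1A as an ordering, and with 10/25/25/40 that ordering is true. A rejection on a transformed scale is a correct rejection of a different null hypothesis. This objection stands, and the figures are not offered as error rates. What remains is that a negative interaction is not evidence for the ordering either, yet the criterion counts it.

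**The choice rule is invented, and a SAP may narrow it.** The protocol names no test, trigger or transformation, and that detail may properly sit in a SAP. The absence of those details is not the complaint. What the protocol does state is that the data decide whether to transform. Reading the data as model residuals does not alter this.

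**No passage defines enhancement as departure from additivity in mm.** True. Choosing mm is a judgement, and floor and ceiling effects in mm can themselves produce interactions. The case for mm is that it is the recorded scale and can be fixed before the data are seen.

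**The planned model is larger than the 2 × 2 illustration.** It has three nicotine and three menthol levels, eight time points and two groups. A positive interaction with 4 degrees of freedom is undefined until contrasts are named. This stands and shapes the fix.

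**Menthol alone may do little.** The low dose is described as barely perceptible, and Section 6 treats intrinsic reinforcement by menthol as open. Then the distortion from the scale is small, as Step 4 shows.

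**Conclusion.** The point holds in two parts of unequal certainty. The first rests on the wording alone: the 1A criterion admits a less-than-additive interaction on any scale, and it can be met when menthol + nicotine is rated below menthol + saline, which contradicts the hypothesis. The second is conditional: with skewed ratings and two positive main effects, letting the distribution pick the scale can create a negative interaction or remove a positive one. Its size rests on assumed means, skewness, correlation and choice rule.

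It would be tempting to extend this to a false claim for 1B. The documents do not support that, because the 1B criterion requires stronger effects in menthol smokers. With additive effects in both groups (10/30/20/40 against 10/30/5/25), at most 0.3% of simulated trials were significant in the 1B direction. The risk for 1B is lost power or a misleading reversed result.

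The change should be made: it is cheap and alters what a positive 1A result would mean. Confidence in the size of the scale effect is moderate.

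**What to change.** 1. **Define support for 1A by named contrasts.** For each menthol dose and each nicotine dose, use (menthol+nicotine − control+nicotine) − (menthol+saline − control+saline). That is 2 × 2 = 4 contrasts per primary item. Require them to be positive, tested after the overall interaction with the Bonferroni correction already planned. Also require menthol + nicotine to exceed all three comparators named in hypothesis 1A.
2. **Fix the scale in advance.** State that these contrasts and the 1B contrast are tested on the 0–100 mm rating whatever the normality check shows. If residuals are markedly non-normal, use robust inference or a bootstrap that resamples whole subjects. Report any transformed analysis as a labelled sensitivity analysis.

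Both parts are needed. In the assumed setting, requiring a positive sign on the chosen scale brings the additive 10/25/25/40 rate below 1% but leaves power for 10/20/20/40 at only 19–35%. Fixing mm as well gives 2–3% and 61–89%.

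The cost is a few sentences and no change to conduct. The downsides are a stricter criterion for 1A, some loss of efficiency if ratings are very skewed, and floor and ceiling effects in mm that must be noted when the result is interpreted.

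### Single-step Bonferroni for the post-hoc comparisons is valid, but Holm's step-down version gives the same error control and shows more reliably which dose pairs differ; the overall 1A decision is essentially unaffected

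*Protocol*

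**What the plan says.** All of this stands in Protocol section 12, Data analysis methods.

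- **Error control.** The main hypotheses are tested at 0.05. For the remaining tests the rule is that "Bonferroni correction will be applied for post-hoc tests". No step-down procedure is mentioned.
- **Criterion for 1A** (under Specific Aim #1). The nicotine-by-menthol interaction must be significant, "with significantly higher response to menthol + nicotine compared to control flavor + nicotine or control flavor + saline". There are two parts: an interaction test at 0.05, and pairwise comparisons whose comparators are joined by *or*. The protocol adds that it expects both doses to show effects and will test for dose dependence.
- **Planning** (Rationale for sample size). "Applying Bonferroni correction and using an alpha level of 0.01", the plan claims 80% power at d'=0.7. It puts the nicotine effect seen earlier above d'=1.0. The interaction is sized "with 30 subjects per group for a total of 60 subjects at 0.05 significance level".

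**The concern.** The pairwise comparisons are more than description: they form the second half of the 1A criterion, and they determine which dose pairs are reported as showing enhancement. With two menthol doses, two nicotine doses and two comparators there are 2 × 2 × 2 = 8 comparisons per DEQ item.

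These eight are of unequal difficulty. The four against control flavor + saline contain the whole nicotine effect and should be easy to reject. The four against control flavor + nicotine isolate what menthol adds and are harder. Single-step Bonferroni holds the harder four at 0.05/8 = 0.00625 whatever happens to the easy four. Holm's procedure would usually clear the easy four first and then begin on the harder ones at 0.05/4 = 0.0125 or looser. Power for the informative contrasts is given up without any gain in error control.

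**Working it through.** **Inputs from the protocol.** Familywise level 0.05; per-comparison level 0.01; d'=0.7; nicotine effect above 1.0 (1.0 used); 30 per group, 60 in total; nicotine and menthol dose both within-subject.

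**Assumptions.** Two-sided tests; d' is a standardised paired difference; eight comparisons per item (the protocol does not list its comparisons); the same menthol increment at every dose pair; menthol adds nothing under saline; independent residuals of variance 0.5 per cell, so that a paired difference has SD 1.

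**1. The plan's own figure.** 0.05/0.01 = 5, so the planning level is single-step Bonferroni for five comparisons. Power of a paired t-test is P(T > t(1−α/2, n−1)), with T noncentral t and noncentrality d√n. At α = 0.01 and d = 0.7:
- n = 30: 85.0%
- n = 60: 99.6%

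Neither is 80%. A paired test with n = 30 reaches 80% at d = 0.662, which rounds to 0.7. The stated figure is therefore compatible with a rounded detectable effect in 30 subjects, and I do not call it wrong.

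**2. The two rules.** Bonferroni rejects when p ≤ 0.05/m. Holm orders the p-values and compares the k-th smallest with 0.05/(m − k + 1), stopping at the first failure. Step one is the same threshold, 0.05/m. The chance of at least one rejection is therefore identical, and any gain is in the second and later rejections.

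**3. Eight comparisons: power for menthol against control flavor at the same nicotine dose** (simulation, paired t-tests).

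| n, menthol effect | Each comparison, Bonferroni → Holm | All four, Bonferroni → Holm |
|---|---|---|
| 30, 0.7 | 80% → 95% | 48% → 85% |
| 60, 0.7 | 99.4% → 99.9% | 98% → 99.8% |
| 60, 0.45 (assumed) | 74% → 90% | 36% → 76% |

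**4. Five comparisons, n = 30, d = 0.662.** Average power over the real effects, Bonferroni to Holm, with correlations between the test statistics of 0 to 0.8:
- all five real: 80% → 88–92%
- three real: 80% → about 84%
- two real: 80% → 82%
- one real: 80% → 80%

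**5. The 1A decision.** Add the nicotine-by-menthol interaction F test at 0.05 to the model of step 3. Require it together with at least one significant comparison against control flavor + nicotine:
- n = 30, d = 0.7: 81.6% → 81.7%
- n = 60, d = 0.7: 99.1% → 99.1%
- n = 60, d = 0.45: 75.2% → 75.4%, where the interaction alone is significant in 75.5%

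The interaction test is what limits 1A.

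**6. Individual dose pairs once the interaction is also required.**
- n = 30, d = 0.7: 68% → 78%
- n = 60, d = 0.45: 59% → 70%

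The gain per dose pair shrinks to about 10 points but remains.

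**The case against.** A reader might infer that the correction decides 1A and that Bonferroni makes a false negative on 1A materially more likely. The protocol does not support this. Its comparators are joined by *or*, so read literally one rejection is enough, and Holm's first step is Bonferroni's. Even if the rejection must be against control flavor + nicotine, the interaction requirement leaves almost nothing to gain (step 5). Nothing in the criterion asks for all four dose pairs to be significant. If every comparator had to be beaten for a claim, each could be tested at the full 0.05 and neither correction would be needed.

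The size of the gain is also open to challenge:
- 1A is not split by cigarette preference, so its sample is 60, and at d'=0.7 Bonferroni already gives over 99% power per comparison.
- The eight-comparison family is inferred; 0.01 points to five.
- The 0.45 is not a protocol figure.
- Equal menthol increments fit poorly with a low dose chosen to be barely noticeable.

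All of this stands. Bonferroni is also valid, prespecified and already built into the power statement.

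What remains is that the protocol itself expects effects at both doses, the setting in which a step-down procedure helps most. Its menthol effect is an expectation carried over from nicotine data, so values below 0.7 are plausible.

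**Conclusion.** The point holds as an optional efficiency gain. Holm's procedure is never less powerful than single-step Bonferroni at the same familywise error, and the protocol gives no reason for preferring the latter. The benefit is confined to the individual dose-pair comparisons: about 15 points each with eight comparisons at n = 30 and d = 0.7, about 16 points at n = 60 if the menthol effect is 0.45, and about 10 points in either case when a significant interaction is also required. With five comparisons at n = 30 it runs from nothing to 12 points, depending on how many effects are real. At n = 60 and d'=0.7 it is negligible. These sizes rest on the assumptions listed with the working; the ordering of the two procedures does not.

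**What to change.** In section 12, under Data analyses, replace "Bonferroni correction will be applied for post-hoc tests" with: *Holm's step-down Bonferroni procedure will be applied to the planned post-hoc comparisons within each DEQ item.* The 0.01 level in the sample-size rationale can stay as a conservative planning figure.

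The cost is one sentence, with no extra subjects and no loss of error control; adjusted p-values are available in standard software. The small drawback is that simultaneous confidence intervals matching Holm's procedure are less simple, though Bonferroni intervals can still be shown beside the Holm-adjusted p-values.
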